4.2 Safeguards to Minimize Risks	23
4.2.1 Participant Population and Screening	23
4.2.2 Minimizing Risks	23
4.2.3 Data and Safety Monitoring Plan	24
4.2.4 Adverse Events	25
4.2.5 Data Quality	27
4.3 Privacy	27
5 Dissemination	28
5.1 Data Sharing Plan	28
5.2 Access to Data	28
6. Protocol Amendment History	29
7. References	30

1. Synopsis

Grant Title:	Optimizing self-monitoring in a digital health intervention for weight loss
Study Description:	This optimization-RCT will examine the unique and combined efficacy of three self-monitoring strategies for weight loss -- tracking dietary intake, tracking steps, and tracking body weight -- all delivered through digital health tools. A 2x2x2 factorial design will be used, resulting in 8 conditions.
Objectives:	To identify the optimal combination of self-monitoring strategies that maximizes weight loss in a 6-month fully digital intervention for adults with overweight or obesity. Aim 1 : Test the unique and combined effects of the three self-monitoring strategies on weight change from baseline to 6 months. Aim 2 : Test the unique and combined effects of the three self-monitoring strategies on change in secondary outcomes from baseline to 6 months, including caloric intake, physical activity, BMI, and health-related quality of life, as well as weight change from baseline to 1 and 3 months, and proportion of participants who achieve $\geq 5\%$ weight loss at 6 months.
Endpoints:	The behavioral intervention is 6 months in length and will not be terminated early based on efficacy. The study is expected to end after our target sample size is reached and the final participant has completed the 6 month intervention and assessment.
Study Population:	The sample (N=176) will consist of adults (ages 18+) with body mass index (BMI) 25.0 to 45.0 kg/m ² from a nationwide sample of the U.S. population.
Phase or Stage:	Multiphase Optimization Strategy: Optimization Phase
Description of Sites:	All study procedures, including recruitment, intervention delivery, and assessments, will take place remotely.
Description of Study Intervention/Experimental Manipulation:	All participants will receive a 6-month behavioral weight loss intervention that is delivered in a fully digital context without human counseling. Core components include a 10% weight loss goal and weekly behavioral lessons and action plans. Participants will be randomized to 1 of 8 conditions that vary in their receipt of 3 self-monitoring strategies. Participants randomized to track their dietary intake will be instructed to do so daily via the Fitbit app, and will receive a tailored calorie goal. Those randomized to track their steps will be instructed to do so daily via an activity tracker (Fitbit Inspire 3), and will receive an adaptive step goal. Participants randomized to track their body weight will be instructed to do so daily via an e-scale (Fitbit Aria Air scale) and will receive a weekly weight loss goal. Weekly tailored feedback on self-monitoring and goals will be provided.
Study Duration:	The intervention will last 6 months. We expect the study will require approximately 18-24 months for recruitment, intervention and data collection.
Participant Duration:	Individual participants will complete study related tasks within 6 months after randomization.

2. Purpose, Background and Rationale

2.1. Brief Summary

This optimization randomized clinical trial (i.e., “optimization-RCT”) will examine three self-monitoring strategies for weight loss -- tracking dietary intake, tracking steps, and tracking body weight -- all delivered through digital health tools. The purpose of the study is to evaluate the combination of these strategies that maximizes 6-month weight loss in the context of a fully digital health intervention for adults with overweight or obesity.

The investigators will recruit 176 total participants to the trial. Recruitment will occur through remote channels. Interested individuals will be directed to an online eligibility screen; those who are eligible will then be invited to attend an initial remote baseline session with study staff to ensure interest and eligibility in the study. The weight loss intervention will last 6 months, and all participants will receive a “core” intervention consisting of goal setting, behavioral lessons, and action plans - all of which will be delivered remotely. Using a $2 \times 2 \times 2$ factorial design, participants will be randomized to receive 0-3 of the self-monitoring strategies. All study tasks will occur remotely, thus, participants never need to come in-person for any intervention or assessment tasks.

Investigators will use the Multiphase Optimization Strategy (MOST) framework to identify the most effective combination of self-monitoring strategies. The factorial design will allow the research team to determine the unique and combined impact of each self-monitoring component on outcomes. The primary outcome is weight change from baseline to 6 months. To complement the main trial, the research team will also randomize half of participants to receive an interactive orientation session, given prior to the consent process, in order to assess its impact on trial retention at 6 months. Overall, the information gathered from this trial will enable the construction of an optimized digital health intervention for weight loss that can be delivered remotely, which, if found to be effective, could have high potential for public health impact.

2.2 Objective

The overall goal is to identify the optimal combination of self-monitoring strategies that maximizes weight loss in a 6-month fully digital intervention for adults with overweight or obesity.

2.3 Aims

Aim 1: Test the unique and combined effects of the three self-monitoring strategies on

weight change from baseline to 6 months (primary outcome).

Aim 2: Test the unique and combined effects of the three self-monitoring strategies on change in secondary outcomes from baseline to 6 months, including caloric intake, physical activity, BMI, and health-related quality of life, as well as weight change from baseline to 1 and 3 months, and the proportion of participants who achieve $\geq 5\%$ weight loss at 6 months.

2.4 Background and Significance

2.4.1 Obesity

Obesity is a significant public health problem. Obesity has become a pervasive health concern in the United States, with rates of 42% among adults¹ and another 30+% with overweight.² Excess weight heightens risk for chronic diseases,³ including type 2 diabetes, and can magnify psychological distress as a result of weight stigma.⁴ Behavioral weight loss interventions that involve frequent in-person meetings, diet and exercise goals, and behavioral strategies are the gold standard for treating overweight and obesity.⁵ These traditional treatments are effective in producing weight loss up to 10%,⁶ but often lack scalability.

2.4.2 Digital Interventions

Remotely-delivered interventions show promise, but need enhanced efficacy. Digital health interventions that deliver treatment remotely seek to minimize burden, decrease costs, and broaden reach, compared to in-person interventions. With widespread penetration of home broadband, regular phones, and smartphones among U.S. adults (77%,⁷ 97%, and 85%,⁸ respectively), digital health tools are increasingly being used in weight loss interventions, with promising efficacy.⁹⁻¹³ Compared to traditional interventions with counseling, fully standalone digital interventions offer greater scalability given lower personnel costs. However, weight loss tends to be modest¹⁴⁻¹⁵; thus, more work is needed to enhance the impact of standalone digital approaches.

2.4.3 Self-Monitoring

Self-monitoring via digital health is effective at facilitating weight loss. Self-monitoring is a well-established method of facilitating weight loss for adults with overweight or obesity.¹⁶⁻¹⁸ It involves tracking a behavior (e.g., diet, exercise) or behavioral outcome (e.g., body weight) and allows individuals to pay attention to their behaviors and gain feedback on how specific actions impact their weight.

2.5 Theoretical Framework

Self-regulation theories, including Social Cognitive Theory and Control Theory, posit that behavior change occurs through comparison of one's behavior to one's goals or past performance.¹⁹⁻²⁰ Self-monitoring is one of the strongest predictors of behavior change²¹ and weight loss²² and is thought to work by increasing self-regulatory skills and self-efficacy for making healthy changes.

However, self-monitoring engagement tends to decline over time with common barriers related to time demands, perceived burden, accessibility challenges, waning novelty, and literacy/numeracy constraints.^{23,24} Fortunately, there are ways to promote self-monitoring engagement by using digital rather than paper based methods of self-monitoring,¹⁶ and by incorporating theory-informed and empirically-supported self-regulation strategies such as goal setting, tailored feedback, and action planning. Meta-analyses have found that the effects of self-monitoring are magnified when adding these strategies.²⁵⁻²⁷ Advantages of using digital platforms for self-monitoring include immediate personalized feedback, reduced tracking time with automated monitoring via devices like fitness trackers and e-scales, and high portability of mHealth tools, which increases the likelihood of use while reducing retrospective errors. A systematic review of 39 randomized trials examined digital self-monitoring strategies used in weight loss interventions and concluded that greater self-monitoring was positively associated with weight loss in over 70% of the reported associations.¹⁶ This pattern was demonstrated across a range of digital health modalities and self-monitored behaviors. In sum, self-monitoring is a theory-informed and evidence-based approach for weight loss that can be delivered via digital tools.

2.6 The Multiphase Optimization Strategy (MOST)

It is important to have interventions that are both efficient and potent, with no extraneous components. Factorial designs can identify active ingredients of an intervention that contribute added impact as well as inactive components that are unnecessarily burdensome and potentially even detrimental. As such, a factorial design can be used to address which combination of self-monitoring strategies maximizes weight loss, and whether any synergistic or antagonistic effects exist, which occur when the combined effect of two or more intervention components is more or less favorable, respectively, than would be expected based solely on main effects.

MOST is an engineering-inspired framework that provides an opportunity for researchers to design effective and efficient multicomponent behavioral interventions.²⁸ MOST involves three phases: Preparation, Optimization, and Evaluation. First, the Preparation Phase consists of understanding gaps in the field, selecting intervention

components to test, and developing a conceptual model. Second, the Optimization Phase consists of conducting a fully powered optimization-RCT to rigorously test the intervention components' unique and combined effects on the outcome of interest. Third, a subsequent Evaluation Phase involves testing the newly optimized intervention versus a comparator in a traditional two-arm evaluation-RCT.

[figure not shown]
2.7 Gaps & Advancing Knowledge in the Field

No study has examined the optimal *combination* of self-monitoring strategies. While the value of self-monitoring has been demonstrated repeatedly, what remains unknown is which self-monitoring domains actually contribute the greatest amount to weight loss, and whether any combinations diminish weight loss and create undue burden. Examining the unique and combined impact of three popular self-monitoring strategies (diet, steps, and body weight) will allow an evidence-based intervention to be constructed that maximizes weight loss while minimizing undue patient burden.

3. Research Plan and Design

The study purpose is to conduct a 6-month optimization-RCT (N=176) using a factorial design to evaluate three self-monitoring components in a remotely-delivered weight loss intervention for adults with overweight/obesity. As shown in the conceptual model (**Figure 1**, below), participants will be randomized to one level of each of the three self-monitoring components: self-monitoring diet (yes, no); self-monitoring steps (yes, no); self-monitoring body weight (yes, no). Each component has an expected mechanism of action (i.e., increase self-monitoring engagement for its respective domain), which, in turn, is expected to enhance self-efficacy and self-regulatory skills, based on Social Cognitive Theory.¹⁹ Together, these putative mediators are expected to improve healthy behaviors and decrease caloric intake, leading to weight loss.

Figure 1. Conceptual Model of the Spark Trial.

3.1 Overview

All participants will receive a core intervention and will be randomized to receive 0-3 self-monitoring components. The intervention is fully digital without human counseling and will last 6 months, with remote assessments at baseline, 1, 3, and 6 months.

3.2 Study Design

This optimization-RCT will use a 2^3 full factorial design (i.e., $2 \times 2 \times 2$) to test three self-monitoring components. As shown in **Figure 2**, below, for each self-monitoring component, half of participants will be assigned to receive it ("Yes") while the other half will not ("No"). In total, participants will be randomized to 1 of 8 experimental

conditions. A factorial trial compares means across *combinations of conditions* in order to test main effects of components and their interactions.²⁸ For example, the main effect of ‘Tracking Diet’ is the mean weight change for the participants who receive this component (i.e., the “Yes’s” in experimental conditions 5-8) versus the mean weight change of those who do not receive it (i.e., the “Nos” in conditions 1-4).

Figure 2. Factorial Design in the Spark Trial.

Experimental Condition	Core	Track Diet	Track Steps	Track Weight
1	Yes	No	No	No
2	Yes	No	No	Yes
3	Yes	No	Yes	No
4	Yes	No	Yes	Yes
5	Yes	Yes	No	No
6	Yes	Yes	No	Yes
7	Yes	Yes	Yes	No
8	Yes	Yes	Yes	Yes

3.3 Study Population

3.3.1 Recruitment

Participants will be recruited through several remote channels across the United States and in the San Francisco Bay Area, which may include the following: a) social media posts (Twitter and Facebook), b) research registries (ResearchMatch.org, a national registry of health research volunteers; ClinicalTrials.gov registry; the Stanford Diabetes Research Center’s registry comprised of adults with pre-diabetes or type 2 diabetes, as well as healthy individuals), c) community advertisements (Nextdoor, Craigslist), and d) university-affiliated research websites. The recruitment phase is expected to span up to 15 months and will accumulate a total of 176 participants. Briefly, eligibility criteria include: adults ≥ 18 years, body mass index (BMI) $25-45 \text{ kg/m}^2$, smartphone ownership, no recent weight loss ≥ 10 lbs., and no condition that contraindicates weight loss (see section 3.3.3 for more details).

Recruitment efforts will target at least 50% racial/ethnic minority group enrollment given that these groups are under-represented in behavioral obesity treatment research.²⁹⁻³⁰ Further, populations who identify as Black and/or Hispanic have disproportionately higher rates of overweight/obesity.^{2,31}

3.3.2 Retention

Retention will be maximized by reimbursing participants for their time spent on the 3- and 6-month remote assessments (\$20 and \$30 e-gift card, respectively) and by providing an additional \$10 e-gift card for completion of all 4 dietary recalls (2 at baseline, 2 at 6 months). Study staff will ask permission to collect multiple phone numbers, email addresses, and family or close friend contact information, and assess preferences for contact methods. Reminder text messages/emails will be sent prior to the remote assessments and follow up with participants via various channels (text, phone, email) if they have yet to complete assessments. Other tactics that we will use to help retain participants include staff available to troubleshoot, personalization of materials, use of technology for self-monitoring, use of a multiple-component intervention (e.g., self-monitoring plus feedback plus goals), and flexibility in participants' completion of remote assessments.

3.3.3 Participant Eligibility Criteria

Table 1. Inclusion and Exclusion Criteria in the Spark Trial.

Inclusion Criteria	
 adults (ages 18+ years) body mass index (BMI) 25.0 to 45.0 kg/m² smartphone ownership willingness to install a mobile app (Fitbit) on their phone access to a personal email account English language proficiency interest in losing weight through behavioral strategies
Exclusion Criteria	
 concurrent enrollment in another weight management intervention loss of ≥ 10 lbs. in the past 6 months current use of a weight loss medication prior or planned bariatric surgery current or planned pregnancy in the trial period currently breastfeeding living with someone else participating in the study hospitalization for a mental health condition in the past 12 months inability to engage in moderate forms of physical activity akin to brisk walking if weight loss is contraindicated or might be impacted by a condition (e.g., end stage renal disease, cancer, schizophrenia, dementia) or medication (e.g., steroids, anti-psychotics) if an individual would be better suited for a more intensive or different type of intervention based on a health condition (e.g.,

	
individuals with history of an eating disorder or cardiovascular event, uncontrolled hypertension, or uncontrolled diabetes mellitus)
 
 • investigator discretion for safety reasons
--	---

3.4 Study Procedures

3.4.1 Screening and Orientation Session

All study procedures will occur through remote means. Recruitment materials will direct interested individuals to an online screening questionnaire (via REDCap) that describes the study and assesses initial eligibility. As part of an embedded experiment called a Study-Within-A-Trial (“SWAT”),³² eligible candidates are then randomized 1:1 to either receive a self-directed orientation session or not receive it. Those assigned to receive it will be prompted to complete a 20-25 minute web-based orientation session consisting of video content and interactive activities designed to set expectations, explain the study rationale and details, visualize the time commitment, and ensure the trial is a good fit for their interests. At the end of the orientation session, those individuals will have the option to sign up for a baseline visit (see preregistration repository: protocol SWAT 211)³³. The orientation session is modeled after the Methods-Motivational Interviewing approach,³⁴ which was developed to increase clinical trial retention.

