3.4.2 Baseline Visit and Randomization

Individuals not randomized to receive the orientation session will receive an email invitation to sign up for a baseline visit. All participants will attend a baseline visit, regardless of orientation session assignment. At this baseline visit (~1-1.5 hours), trained study staff will confirm eligibility and describe study procedures. If individuals are interested in participating, study staff will obtain informed consent to assure that they fully understand the demands and purpose of the study before enrolling. Next, study staff will help participants create a Fitbit account and download the Fitbit app. Study staff will then administer a web-based dietary recall, an oral health literacy assessment, and a web-based baseline survey. Once the survey is completed, study staff will mail all participants an e-scale to obtain baseline weight measurement. Once the e-scale is delivered, participants will receive an email that provides information on syncing their e-scale with the Fitbit app, and will be prompted to weigh themselves the following morning using a standardized protocol. Within the week after the baseline visit, a 2nd unannounced web-based dietary recall will be administered, with reminders sent if it is not completed.

Once the weight assessment is completed, participants will be randomized to 1 of 8 experimental conditions via an algorithm on REDCap. Study staff will mail an activity

tracker (Fitbit Inspire 3) within 2 business days to those randomized to the conditions with self-monitoring of steps (i.e., conditions 3, 4, 7, 8; **Figure 2**, above). Once the tracker is delivered, participants will receive instructions for syncing the tracker with the Fitbit app. Study staff will be available to troubleshoot with device syncing, as needed. Then, the weight loss intervention will begin -- participants will receive an automated email describing their assigned intervention.

Following recommendations for factorial designs,³⁵ we will randomize participants to the 8 conditions using restricted randomization. We will stratify by sex assigned at birth and use permuted block randomization with a block size of 8. The allocation sequence was generated using SAS by the study's statistician ([name]) and stored in REDCap. Study staff will use REDCap to implement the random allocation sequence (i.e., randomize a participant) once both the baseline weight and web-based baseline surveys are submitted.

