3.4.3 Screen Failures

Participants who consent but then become ineligible prior to randomization will be asked to withdraw from the study and will not be randomized. Examples would include if a participant's baseline weight collected via the study-issued e-scale (after consenting) puts them out of range on the BMI criterion (i.e., no longer being in the 25.0-45.0 kg/m² range), which may occur when their initial BMI that was calculated using self-reported weight put them on the edges of that range), or if a participant reports a pregnancy or exclusionary medical condition in the period between consent and randomization. All other reports of changes to eligibility criteria will be decided upon by study investigators prior to randomization.

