3.8.2 Secondary and Exploratory Outcomes

Secondary outcomes include the following: 6-month change in caloric intake, physical activity, BMI, and health-related quality of life; 1- and 3-month weight change; and the proportion of participants achieving clinically significant weight loss ($\geq 5\%$ at 6 months). We will also examine additional outcomes: self-monitoring engagement rates and their relation to 6-month weight change; 6-month changes in diet quality; 6-month changes in step count among those assigned to self-monitor steps; the impact of potential moderators on 6-month weight change to determine for whom each self-monitoring strategy works best; and the impact of the orientation session on 6-month retention. In exploratory analyses, 6-month weight change data will be disaggregated by sex.

Caloric intake will be assessed via the Automated Self-Administered 24-hour (ASA24) Dietary Assessment Tool (version 2022 and 2024- beginning in April 2025), which is a free web-based tool developed by the National Cancer Institute.⁴⁹ Participants will be asked to complete a total of four 24-hour dietary recalls, including two at baseline and two at 6 months. At both time points, we will request one weekday recall and one weekend day recall. We will send up to 4 reminders per time point. We will exclude from our analyses any recalls with outliers of daily caloric intake reported as a minimum of <800 kcal for everyone, and a maximum of >4400 kcal for women and >5700 kcal for men, in accordance with ASA24 recommended procedures.⁵⁰ To compute caloric intake at each time point, we will calculate the mean of the weekday recall and the weekend-day recall; if only one recall is available at a given time point, we will use that

value. Diet quality will be assessed using the Healthy-Eating Index-2020,⁵¹ calculated from ASA24 data.

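### Does randomising candidates to the orientation session before consent undermine its comparison of 6-month retention?

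*Protocol*

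**What the plan says.** Protocol 3.4.1 places the randomisation straight after the online eligibility questionnaire: "eligible candidates are then randomized 1:1 to either receive a self-directed orientation session or not receive it". The session lasts 20-25 minutes, and one of its stated aims is to "ensure the trial is a good fit for their interests". The two arms then reach booking by different routes. For the session arm, "At the end of the orientation session, those individuals will have the option to sign up for a baseline visit". For the other arm, section 3.4.2 says: "Individuals not randomized to receive the orientation session will receive an email invitation to sign up for a baseline visit". Consent is taken at the baseline visit, and section 3.4.3 allows further loss after it: "Participants who consent but then become ineligible prior to randomization will be asked to withdraw from the study".

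Section 2.1 describes the same experiment more briefly. The team will "randomize half of participants to receive an interactive orientation session, given prior to the consent process", and the purpose is given as "in order to assess its impact on trial retention at 6 months". Section 3.8.2 lists "the impact of the orientation session on 6-month retention" among the additional outcomes, after the secondary ones, and names no analysis population for it.

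Section 3.11 leaves statistical analysis to the separate SAP, and section 3.4.1 refers to the preregistered protocol SWAT 211. Neither document was available for this review.

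**The concern.** Candidates are randomised, but trial retention exists only for those who go on to enrol. Enrolment comes after this randomisation, and the session could influence it. A comparison of retention among enrollees therefore conditions on a post-randomisation event. It mixes two things: who chose to enrol, and whether the session made any given person more likely to stay.

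Taken alone, that comparison also hides what the session costs in candidates. It could favour the session while fewer of the candidates offered it end up enrolled and retained.

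The sections also seem to disagree on the randomised unit. Section 2.1 speaks of half the participants and section 3.4.1 of eligible candidates. A 1:1 split of candidates gives an even split of enrollees only if both arms enrol at the same rate. Read literally, section 2.1 points to the enrolled population, which is the one exposed to selection.

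**Working it through.** The protocol states no sample size, power, retention rate or enrolment rate for this experiment, so there is no figure to reproduce. There are two checks: how the text reads, and how large the effect could be.

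**The text.** The order of events is online screen, orientation randomisation, booking, baseline visit with consent, baseline weight, then randomisation to the 8 conditions (3.4.1 to 3.4.3). Section 2.1 fits this order, because the same sentence puts the session before consent. Section 3.4.2 also uses the word participants for everyone attending the baseline visit, before consent has been sought. So section 2.1 can be read as a 1:1 allocation of people entering the study process. It need not be a claim that 88 of the 176 enrolled will have had the session.

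**The possible size.** All rates below are assumptions. Candidates are of two types: a share p who are committed, with retention rc, and the rest, with retention rl. Their enrolment rates are ec and el. The session changes nobody's retention.

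- Enrolled per candidate: E = p·ec + (1−p)·el
- Enrolled and retained per candidate: Y = p·ec·rc + (1−p)·el·rl
- Retention among enrollees: Y/E
- Session arm's share of the 176: E1/(E0+E1)

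In the no-session arm ec = el = 0.60 throughout. Rows A to C use p = 0.6, rc = 0.9, rl = 0.7; rows D and E use p = 0.5, rc = 0.9, rl = 0.6. Results are session vs no session.

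| Case | Session ec / el | Y/E | Difference (SE), points | Y | Session share | P(p<0.05) |
|---|---|---|---|---|---|---|
| A | 0.60 / 0.60 | 82.0% vs 82.0% | 0 | 49.2% vs 49.2% | 50% | nominal |
| B | 0.40 / 0.40 | 82.0% vs 82.0% | 0 | 32.8% vs 49.2% | 40% | nominal |
| C | 0.60 / 0.40 | 83.8% vs 82.0% | +1.8 (5.7) | 43.6% vs 49.2% | 46% | 6% |
| D | 0.60 / 0.30 | 80.0% vs 75.0% | +5.0 (6.3) | 36.0% vs 45.0% | 43% | 12% |
| E | 0.60 / 0.15 | 84.0% vs 75.0% | +9.0 (6.1) | 31.5% vs 45.0% | 38% | 31% |

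Case C in full:

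- Session arm: E = 0.6×0.60 + 0.4×0.40 = 0.52, and Y = 0.36×0.9 + 0.16×0.7 = 0.436. So Y/E = 0.838.
- No-session arm: E = 0.60, and Y = 0.60×(0.6×0.9 + 0.4×0.7) = 0.492. So Y/E = 0.820.
- Session share: 0.52/1.12 = 0.464, about 82 vs 94 people.
- SE = √(0.838×0.162/82 + 0.820×0.180/94) = 0.057.

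A second set of assumptions gives the same pattern. Take two equal halves retained at 95% and 70%, with 50% of the no-session arm enrolling and the session halving enrolment of the second half. Retention among enrollees is 86.7% vs 82.5% (+4.2 points). Enrolled and retained per candidate is 32.5% vs 41.25%, about 8.8 points lower.

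The direction is assumed as well. Exchanging the two arms' enrolment rates in case C turns +1.8 into −1.8 points and reverses the yields.

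**The case for a change.** The strongest argument for a change does not depend on the unstated denominator. The protocol itself fixes the randomised unit (candidates) and an outcome defined only for enrollees. It gives the arms different routes to booking, and it describes a session meant to affect fit. Selection is then a natural consequence of the design, and the two denominators can point in opposite directions. The remedy would be cheap: one sentence on the population and one table by arm. Screening, randomisation and status tracking all run in REDCap (3.4.1, 3.12), so the counts should exist.

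Much of this stands. Retention among enrollees should not be read as an effect on individuals, and enrolment by arm belongs beside it in any report. It does not show an error in the protocol, for three reasons.

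- **Nothing is wrongly fixed.** No section restricts the comparison to enrollees. The analysis population for an additional outcome is commonly left to the SAP, and section 3.4.1 already cites the experiment's own protocol.
- **Selection is part of the intervention.** The session is described as setting expectations and checking fit, on a model developed to raise retention. E and Y are each arm-level quantities over randomised candidates, so the contrast of Y/E is a fair comparison of recruiting with and without the session. A significant result produced by selection is misleading only if the aim is an individual-level effect, and the protocol does not state that aim.
- **The difference in units is loose summary wording.** The fuller description in 3.4.1 is unambiguous and governs.

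**Conclusion.** No change to the plan follows. The structural observation is correct, but the concern comes down to detail that the SAP or SWAT 211 may hold, plus an imprecise word in a summary section. An analyst would handle it in the ordinary way: report the flow of candidates by arm, and describe retention among enrollees as conditional on enrolment.

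The size is unknown. The range of 0 to 9 points rests wholly on assumed rates. The top of that range needs the session to cut enrolment of less-committed candidates by three quarters (60% to 15%). In the mildest case with unequal selection, the chance of p<0.05 is about 6%, against a nominal 5%.

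The primary result is not exposed. Randomisation to the 8 conditions comes after enrolment and baseline weighing, so any selection by the session acts before that allocation and does not bias the weight comparisons.

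The conclusion assumes that the SAP and SWAT 211 do not themselves present retention among enrollees as an individual-level effect. Nothing in the protocol suggests that they do.
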